#### 4.3 Digits displayed for the statistics

Item	Digits displayed
Measured value	Same digits as significant digits
Number of cases	Integer
Percentage, ratio	one decimal place
BMI	two decimal places
Summary statistics	Number of patients
	Mean, median
	Standard deviation, Standard error
	Minimum, maximum
	95% confidence interval
Testing/estimation	P value

Significant digits: The standard number of digits after the decimal point of the data value. If the data value is not standardized, the maximum number of digits will be adopted.

#### 4.4 Significant protocol deviation

Significant protocol deviations are out of the scope of this document.

#### 4.5 Definition of clinically significant abnormal changes in laboratory data

Not applicable.

#### 4.6 Software used for analysis

Refer to Section "4. Statistical Analysis Environment" of "Statistical Analysis Procedures Ver. 1.0" (February 5, 2021), separately.

#### 4.7 SAS Code

- SAS Code for implementing Cox regression model is shown below.

```
ods output ParameterEstimates = [OUTPUT];
proc phreg data = [DATASET];
  class [GROUP] [THERAPY];
  model [TARGET] * [CENSOR FLG](0) = [GROUP] [THERAPY] / rl alpha = 0.05;
run;
```

- SAS Code for implementing MMRM model is shown below.

```
proc mixed data = [DATASET];
  class [SUBJECT] [VISIT] [GROUP];
  model CHG = BASE [VISIT] [GROUP] [VISIT] * [GROUP] /ddfm = KR;
  lsmeans [GROUP]* [VISIT];
  repeated [VISIT]/ subject = [SUBJECT] type = UN;
```

run;

- SAS Code for implementing analysis using generalized estimating equation is shown below.

```
proc genmod data = [DATASET];
  class [SUBJECT] [VOLUME] [GROUP];
  model CHG = [GROUP] [VOLUME] [GROUP]* [VOLUME] ;
  lsmeans [GROUP]* [VOLUME];
  repeated subject = [SUBJECT] type = UN or CS;
run;
```

- SAS Code for implementing analysis using MMRM model (cLDA method) is shown below.

\* The coefficient of Estimate must be changed to suit the data.

\*The value of DIF3, DIF5, and DIF10 in the active group is 1 at each time point, otherwise 0.

```
proc mixed data = [DATASET] order = internal;
  class AVISITN(ref = "1") USUBJID;
  model AVAL_ = AVISITN DIF3 DIF5 DIF10/noint s ddfm = kr;
  random USUBJID;
  /* difference between groups in each time point*/
  estimate "Diff (NPC-26 - Placebo) Day3" DIF3 1 /cl;
  estimate "Diff (NPC-26 - Placebo) Day5" DIF5 1 /cl;
  estimate "Diff (NPC-26 - Placebo) Day10" DIF10 1 /cl;
  /* Mean CHG in each time point in each group */
  estimate "LSMean of Change from BL (Placebo) Day3" AVISITN 1 0 0 -1 /cl;
  estimate "LSMean of Change from BL (Placebo) Day5" AVISITN 0 1 0 -1 /cl;
  estimate "LSMean of Change from BL (Placebo) Day10" AVISITN 0 0 1 -1 /cl;
  estimate "LSMean of Change from BL (NPC-26) Day3" AVISITN 1 0 0 -1 DIF3 1 /cl;
  estimate "LSMean of Change from BL (NPC-26) Day5" AVISITN 0 1 0 -1 DIF5 1 /cl;
  estimate "LSMean of Change from BL (NPC-26) Day10" AVISITN 0 0 1 -1 DIF10 1 /cl;
  /*Mean AVAL in each time point in each group */
  estimate "LSMean (Placebo) Day1" AVISITN 0 0 0 1 /cl;
  estimate "LSMean (Placebo) Day3" AVISITN 1 0 0 0 /cl;
  estimate "LSMean (Placebo) Day5" AVISITN 0 1 0 0 /cl;
  estimate "LSMean (Placebo) Day10" AVISITN 0 0 1 0 /cl;
  estimate "LSMean (NPC-26) Day1" AVISITN 0 0 0 1 /cl; *This is same as in common with
Placebo;
  estimate "LSMean (NPC-26) Day3" AVISITN 1 0 0 0 DIF3 1 /cl;
  estimate "LSMean (NPC-26) Day5" AVISITN 0 1 0 0 DIF5 1 /cl;
  estimate "LSMean (NPC-26) Day10" AVISITN 0 0 1 0 DIF10 1 /cl;
run;
```

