2 Observation and Examination Schedule

Item	Screening	Date of allocation	Observation period ⁵⁾												Discontinuation/ Exit Test ⁶⁾
			Day 0	Day 1	Day 2	Day 3	Day 4	Day 5	Day 6	Day 7	Day 8	Day 9	Day 10	Day 11 ~14	Day 15 ~28
Acceptable window	To Day 0	-2 days ⁷⁾	—	—	—	—	—	+1 day ⁷⁾	—	—	—	—	—	—	+1 day
Informed consent	●														
Medical history/current medical conditions	●														
Subject characteristics	●														
Height and weight	●														
Inclusion and exclusion criteria	●														
Percutaneous oxygen saturation (SpO2)	●														
Allocation		●													
Study drug administration ¹⁾			●	●	●	●	●	●	○	○	○	○	○		
7-point ordinal scale ²⁾			●	●	●	●	●	●	●	●	●	●	●	●	
Oxygen requirement			●	●	●	●	●	●	●	●	●	●	●	●	
Arterial blood gas analysis (PaO2, PaCO2, A-aDO2, others)			● ³⁾					●							●
Inflammatory markers, cytokines			● ³⁾		●		●								●
Chest HRCT or plain chest CT or Chest X-ray			●					●							●
Physical examination			●					●							●
Vital sign			●					●							●
12-lead ECG			●					●							●
Laboratory tests (blood chemistry, hematology and urinalysis)			●					●							●
Pregnancy test (urine or blood sample)			●												
adverse events ⁴⁾				●									●		
Concomitant medication/therapy		●	—									●			

● : Will be performed in all the subjects ○ : Will be performed only in the subjects who continue to receive the study drug after Day 5.

1) Inhalation administration will be started on the morning of Day 1 and performed twice daily (morning, evening) for 5 days, in principle (up to 10 days).

2) Will be evaluated every day during the period between Day 1 and Day 28. Use or no use of a ventilator will be included in this evaluation.

3) Will be performed prior to study drug administration.

4) Only the adverse events that have occurred until Day 14 after the start of study drug administration. may be collected and entered in the electronic case report form. Serious adverse events related to the study drug administration will be collected until Day 28.

- 5) Assessment of efficacy on the 7-point ordinal scale and oxygen requirement will be performed after completion of the second dose (inhalation) of the day.
- 6) Will be performed on the day of discontinuation if study drug administration has been prematurely discontinued before Day 5, or on the day of the last dose in the case that the last day is not Day 5.
- 7) Except 7-point ordinal scale and oxygen requirement.

3 Study Administrative Structure

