5.2 Endpoints

5.2.1 Efficacy endpoints

Primary efficacy endpoint

Number of days to achieve at least 2-rank improvement on a 7-point ordinal scale from baseline until Day 28.

[Rationale]

A 7-point ordinal scale is one of the commonly used scales for assessment of drugs used in the clinical studies of COVID-19 and was set as an index to numerically assess the improvement effect of sargramostim administration on the disease condition. Taking the study drug administration period (5 days, in principle [up to 10 days]) in this study, the usual period for treatment and hospital stay of COVID-19 patients in Japan, and the results of other clinical studies into account, the required number of days to achieve at least 2-rank improvement on a 7-point ordinal scale from baseline until Day 28 was set as the primary efficacy endpoint.

Secondary endpoints

- (1) Changes in alveolar-arterial oxygen partial pressure gradient (A-aDO₂) from baseline to Day 5 and the end of administration.
- (2) Number of days until discharge from baseline (days for shifting to Category 7 on a 7-point ordinal scale).
- (3) Proportion of subjects whose category has shifted to Category 1 or 2 on a 7-point ordinal scale from baseline until Day 28.
- (4) Changes in pulmonary inflammatory findings from baseline to Day 5 and the end of administration.
- (5) Changes in arterial blood-gas parameters (partial pressure of oxygen [PaO₂] and partial pressure of carbon dioxide [PaCO₂]) from baseline to Day 5 and the end of administration.
- (6) Changes in inflammatory markers and cytokines from baseline to the end of administration.
- (7) Distribution and proportion of each category on 7-point ordinal scale on Day 14 and Day 28.
- (8) Distribution and proportion of each category of oxygen requirement until Day 14.
- (9) Other exploratory items (details will be specified separately in the statistical analysis plan).

[Rationale]

- (1) An interim analysis of the clinical study ¹¹ being conducted in Belgium in COVID-19 patients (20/ target sample size of 80) suggested the efficacy of sargramostim for A-aDO₂, an index of arterial oxygen uptake (see 6.3 Rationale for dosage and administration). Therefore, changes in A-aDO₂ was set as a secondary endpoint in this study. Since the duration of the study drug administration in this study is set to be "5 days, in principle (up to 10 days)", both the periods of "Day 5 from baseline" and "End of administration from baseline" were set for assessment.

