### 2.1.2.10 Efficacy Evaluation

#### 2.1.2.10.1 Primary endpoint

- (1) Analysis set : FAS, PPS
- (2) Analysis item : period to the first improvement by at least 2-rank between baseline and Day 28 on a 7-point ordinal scale.
- (3) Time point : Day 0 to Day 28
- (4) Analytical method : The following analysis will be performed.
  - 1) As the main analysis, the improvement rate will be estimated by treatment group using Kaplan-Meier method, and the comparison between groups using the log-rank test with a significance level of 5% will be performed as well. In addition, assessment using Cox's proportional hazards model with the presence or absence of concomitant antiviral drugs for COVID-19 as a covariate will be performed. Definitions of the events and censoring are presented in Table 2.3.

Table 2.1 7-Point ordinal scale

Category	ordinal scale
1	Have died
2	Use an invasive ventilator or ECMO
3	Use a noninvasive ventilator or high-flow oxygen supply device
4	Require oxygen supply
5	Do not require oxygen supply but require continuous therapy (related to COVID-19 or others)
6	Do not require both oxygen supply and continuous therapy
7	Have been discharged from hospital

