2) For patients who were categorized in each category on a 7-point ordinal scale on Day 14 (or at the last observation the point) and Day 28 (or at the last observation time point between Day 15 and Day 27), the p-values (Wilcoxon's rank sum test) of the differences between groups will be calculated.

2.1.2.10.2.9 Distribution and proportion of patients in each category of oxygen requirement until Day14

(1) Analysis set : FAS

(2) Analysis item : oxygen requirement

(3) Time point : Day 0 to Day 14

(4) Analytical method :

1) The number of patients and the proportion in each category on the oxygen requirement shown in Table 2.2 until Day 14 will be summarize by treatment group and by time point (number of patients, %). In addition, a bar chart showing the percentage of each category will be prepared by treatment group and by time point.

2) For patients who were categorized in each category on the oxygen requirement on Day 5 and Day 14, the p-values (Wilcoxon's rank sum test) of the differences between groups will be calculated.

Table 2.2 Oxygen requirement

Category	Ordinal scale
1	Require oxygen supply of 4 L/min or more using oxygen mask
2	Require oxygen supply of 2 L/min or more using nasal cannulas
3	Require oxygen supply of less than 2 L/min using nasal cannulas
4	Do not require oxygen supply but feel shortness of breath during walking or moving
5	Do not require oxygen supply and do not feel shortness of breath during walking or moving

Table 2.3 Definition of event/censoring in Time to event analysis

Analysis item	Event/ Censoring	Definition of event/censoring	Period

 
Period to the first improvement by at least 2-rank between baseline and Day 28 on a 7-point ordinal scale 
 
Period from baseline to the day of discharge
 
Period from baseline to shifting to Category 6 or 7 on a 7-point ordinal scale
 
Period from baseline to shifting to Category 5 on a 7-point ordinal scale
 
Period to from baseline to improvement by 1 rank or more on a 7-point ordinal scale
 
 
 
	Event	A patient who developed an event	Period until the onset of the first event
	Censoring	A patient who completed the study without any event	Period until the last observation day
		A patient who discontinued or died	Censored after complementing 29 days*

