#### **2.1.2.12 Interval estimation and level of significance**

As a general rule, the significance level of 5% two-sided will be applied, and a two-sided 95% confidence coefficient ( $1-\alpha$ ) will be applied for the interval estimation.

[figure not shown]

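### The Cox code for the primary endpoint names no tie method, so SAS's default (Breslow) pulls the hazard ratio slightly towards 1; a minor point with a free fix

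*SAP*

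**What the plan says.** Protocol 5.2.1 defines the primary endpoint as "Number of days to achieve at least 2-rank improvement on a 7-point ordinal scale from baseline until Day 28". Note 2 to the schedule in Protocol 2 says of the scale: "Will be evaluated every day during the period between Day 1 and Day 28". Event times are therefore whole days, with at most 28 distinct values.

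SAP 2.1.2.10.1 plans three things for this endpoint:

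- Per-arm Kaplan-Meier estimates: "the improvement rate will be estimated by treatment group using Kaplan-Meier method".
- The test that carries the primary decision: "comparison between groups using the log-rank test with a significance level of 5% will be performed as well".
- A Cox model introduced as an addition: "assessment using Cox's proportional hazards model with the presence or absence of concomitant antiviral drugs for COVID-19 as a covariate will be performed".

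The code for the Cox model is in SAP 4.7: "model [TARGET] * [CENSOR FLG](0) = [GROUP] [THERAPY] / rl alpha = 0.05". After the slash it asks only for risk limits and their alpha level. Neither document says how ties are to be handled. SAP 4.6 refers to a separate procedures document for the software environment; that document is not part of the material.

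**The concern.** When PROC PHREG is given no `TIES=` option it uses the Breslow approximation. That is adequate when ties are rare, but it biases the log hazard ratio towards zero when many patients share an event time. Here nearly all of them do.

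The hazard ratio matters because it is the only between-arm effect size planned for the primary endpoint: no difference in medians or in Day 28 improvement rates is specified. It is also the only analysis of that endpoint that adjusts for antiviral use. The same code would serve the FAS and PPS runs, the subgroup Cox models (SAP 2.1.2.15) and the exploratory re-run of the primary analysis with an altered end-of-treatment rule (SAP 2.1.2.10.2.10, item 1). Run as printed, the code understates an effect in either direction, harm as well as benefit.

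**Working it through.** **Inputs.** Protocol 18 gives 40 active and 20 control patients, normal times with means 10 and 14 days, a common SD of 4.5, and a stated log-rank power of 82.1%. SAP 2.1.2.12 says "the significance level of 5% two-sided will be applied". SAP Table 2.3 treats discontinued or dead patients as "Censored after complementing 29 days". Not in the documents, and assumed here: exponential and Weibull shapes, a 50/50 antiviral covariate, 10% discontinuation, and 20% never improving.

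**Step 1: the plan's own figure.** In 5,000 simulated trials on unrounded, uncensored normal times, log-rank power is 82.3%, against 82.1% stated. With times rounded up to whole days and cut at Day 28 it is 83.1%, so rounding does no harm to the log-rank test.

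**Step 2: density of ties.** On whole days the planning model gives on average 60.0 events on 19.2 distinct days, or 60.0/19.2 = 3.1 per day. The largest tie is about 8, and 92% of events are tied. With exponential times (medians 10 and 14) there are 49.3 events on 21.5 days, or 2.3 per day, and 84% are tied.

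**Step 3: what the option changes.** Take a day with d events (set D) and risk set R, and let θ = exp(βx). The partial-likelihood denominators are:

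- Breslow: (Σ_R θ)^d
- Efron: Π over k = 0,…,d−1 of (Σ_R θ − (k/d) Σ_D θ)

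Breslow keeps all d patients in the risk set for each of that day's d events. The faster arm then looks more at risk than it was, and β shrinks.

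**Step 4: size.** Shrinkage = 1 − b(Breslow)/b(reference). In 3,000 trials of the planning model (antiviral covariate omitted) the mean log hazard ratios were 0.830 unrounded, 0.819 Efron and 0.767 Breslow, that is, hazard ratios of 2.29, 2.27 and 2.15.

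- Breslow against Efron: 1 − 0.767/0.819 = 6.3%
- Breslow against unrounded: 1 − 0.767/0.830 = 7.6%
- Efron against unrounded: 1 − 0.819/0.830 = 1.3%, which is the cost of rounding and is not recoverable

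Median hazard ratios in other runs:

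| Scenario | Unrounded | Efron | Breslow | Log HR shrinkage, Breslow vs Efron |
|---|---|---|---|---|
| Normal, 10 vs 14 (repeat run) | 2.26 | 2.24 | 2.13 | 6.5% |
| Exponential, medians 10/14 | 1.39 | 1.39 | 1.38 | 2.7% |
| Weibull shape 1* | 1.346 | 1.348 | 1.337 | 2.2% |
| Weibull shape 2* | 1.548 | 1.555 | 1.526 | 3.7% |
| Weibull shape 3* | 1.718 | 1.716 | 1.654 | 5.8% |
| Weibull shape 2*, no effect | 0.992 | 0.997 | 1.001 | none systematic |

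*With the antiviral covariate and 10% discontinued and censored at day 29.

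Without discontinuation, Weibull shapes 1, 2 and 3 with medians 10/14 give Breslow shrinkage of 3%, 6% and 9%, and Efron at most 1.2%. If 20% of patients never improve, the normal-model shrinkage falls from 7.4% to 3.3% (hazard ratio 1.40 Breslow, 1.41 Efron).

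**Step 5: against sampling error.** In the planning model the shift is 0.819 − 0.767 = 0.052, with a standard error of 0.29; 0.052/0.29 = 0.18. At Weibull shape 3 without discontinuation, Breslow's bias against the true log hazard ratio is −0.078, and 0.078/0.30 = 0.26. So the shift is at most about a quarter of a standard error.

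**Step 6: the Cox Wald test.** Planning-model power was 78.6% Breslow against 81.6% Efron, and in a repeat run 77.8% against 81.0%. With exponential times it was 16.0% against 17.2%. In a run that also recorded the log-rank test, the figures were log-rank 83.9%, Efron 81.8% and Breslow 77.9%. There the log-rank test was significant while the Cox Wald test was not in 6.0% of trials with Breslow and 2.1% with Efron. The two tie methods disagreed on significance in 3.9%.

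**The case against.** Most of the case for leaving the code alone is factually right, and it fixes how much weight the point can bear.

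- **The primary decision is not at risk.** A reader might infer that the trial's main result is biased. It is not: the log-rank test and the Kaplan-Meier curves do not use the `TIES` option.
- **The interval is not misleading.** Under proportional hazards with Weibull shapes 1, 2 and 3, the Breslow 95% interval covered the true log hazard ratio in 95.1%, 96.6% and 96.3% of trials (Efron 94.3%, 95.8% and 95.6%).
- **The planning model is unfavourable to Breslow.** It has a large effect and nearly everyone improves. Its hazards are also not proportional, so no single true ratio exists and the 6-8% is relative to other estimates. Smaller effects or non-responders bring the shrinkage to about 3%.
- **Ties do not explain the whole gap between the Cox and log-rank tests.** With 83.9%, 81.8% and 77.9%, the gap is 83.9 − 77.9 = 6.0 points, and 83.9 − 81.8 = 2.1 of them remain under Efron.
- **The hazard ratio is not the trial's only effect estimate.** It is the only between-arm contrast for the primary endpoint. Per-arm improvement rates are also planned, and several secondary endpoints have estimated differences with intervals.
- **The shift cannot manufacture efficacy**, since there is no systematic movement when the true ratio is 1.

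What does not follow is that the default should stay. Shrinkage understates harm as readily as benefit, and Efron removes nearly all of it at no cost.

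**Conclusion.** The point holds as a minor one. Executed as printed, SAP 4.7 gives a hazard ratio slightly too close to 1. The log hazard ratio is about 6-8% too small in the planning model, about 3% with exponential times or 20% non-responders, and up to about 9% at Weibull shape 3. The Cox Wald test gives up about 1-4 points of power against Efron. No conclusion about the primary test or the validity of the trial follows.

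This rests on the PHREG default being Breslow, on times being analysed in whole days as the schedule implies, and on no tie method being fixed in the separate procedures document. The non-normal shapes, the discontinuation rate and the non-response rate are assumptions, used only to show the range.

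**What to change.** Add `TIES=EFRON` (or `TIES=EXACT`) to the MODEL statement in SAP 4.7, and name the method in SAP 2.1.2.10.1. Apply it to every Cox run: FAS, PPS, the subgroup models and the exploratory re-run of the primary analysis. If the procedures document cited in SAP 4.6 already fixes the tie method, cite it at that point.

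Make the change before the allocation code is released, because the two methods can disagree on whether the interval excludes 1 (3.9% of planning-model trials), and a later choice could look data-driven. The cost is one SAS option and one sentence; data collection, sample size and the primary test are unaffected.

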#### 2.1.2.10.2 Secondary endpoints

##### 2.1.2.10.2.1 Changes in alveolar-arterial oxygen difference (A-aDO2) from baseline to each time point

- (1) Analysis set : FAS
- (2) Analysis item : measured values and changes in A-aDO2 (values at each time point- those at Day1)
- (3) Time point : Day 1, Day 3, Day 5, Day 10, at discontinuation/completion of treatment

(4) Analytical method :

- 1) Summary statistics (number of patients, arithmetic mean, standard deviation, median, minimum, maximum) for measured values and changes will be calculated by treatment group and by time point. In addition, a chart for the mean  $\pm$  standard deviation over time and box-and-whisker plot will be prepared by treatment group.
- 2) Estimated values of the differences between groups, 95% confidence intervals, and p-values (Day 3, Day 5, Day 10) will be calculated using mixed effect model for repeated measures (cLDA method) by time point with the measured values as the response variable, time point, treatment group, and treatment group \* time point as the fixed effects, and patients as the random effect, setting that both groups have the common mean value on Day 1. In addition, estimated values and 95% confidence intervals over time will be prepared by treatment group.
- 3) Estimated values of the differences between groups, 95% confidence intervals, and p-values (Day 5, at discontinuation/completion of treatment) will be calculated using mixed effect model for repeated measures with the measured values and changes as the response variable, baseline values as the covariate, time point (Day 1, Day 5, at discontinuation/completion of treatment), treatment group, treatment group \* time point as the fixed effects, and patients as the random effect. In addition, a chart for the estimated values and 95% confidence intervals over time will be prepared by treatment group.
- 4) The number of patients of whom changes from baseline (Day 1) decreased (improved) by 33% or more and the proportion will be calculated by treatment group and by time point (number of patients, %), and the p-values (Fisher's exact test) will be calculated.

2.1.2.10.2.2 Period from baseline to the day of discharge (days until shifting to Category 7 on a 7-point ordinal scale)

- (1) Analysis set : FAS
- (2) Analysis item : period from baseline to the day of discharge (time point - Day 0)
- (3) Time point : Day 0 to Day 28
- (4) Analytical method :

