#### 2.1.2.10.2.6 Changes from baseline in arterial blood gas values (PaO2, PaCO2, pH) to each time point.

(1) Analysis set : FAS

(2) Analysis item : measured values and changes in arterial blood gas (each time point - Day 1)

(3) Time point : Day 1, Day 3, Day 5, Day10, at discontinuation/completion of treatment

(4) Analytical method :

- 1) Summary statistics (number of patients, arithmetic mean, standard deviation, median, minimum, maximum) for measured values of arterial blood gas and changes from baseline to each time point will be calculated by treatment group and by time point. In addition, a chart for changes in the mean  $\pm$  standard deviation over time will be prepared by treatment group.
- 2) Estimated values of the differences between groups, 95% confidence intervals, and the p-values (Day 3, Day 5, Day 10) will be calculated using mixed effect model for repeated measures (cLDA method) with the measured values as the response variable, time point, treatment group, and treatment group \* time point as the fixed effects, and the patients as the random effect, setting that both groups have the common mean value on Day 1. In addition, a chart for changes in the estimated values and 95% confidence intervals over time will be prepared by treatment group.
- 3) Estimated values of the differences between groups, 95% confidence intervals, and the p-values (Day5, at discontinuation/completion) will be calculated using mixed effect model for repeated measures with the measured values of arterial blood gas and the changes from baseline to each time point as the response variables, baseline values as the covariate, time point, treatment group, and treatment group \* time point as the fixed effects. In addition, a chart for estimated values and 95% confidence intervals over time will be prepared by treatment group.
- 4) The number of patients and the proportion according to implementation status of arterial blood gas analysis (implemented, implemented while supplementing oxygen because supplementing oxygen could not be suspended, not implemented, not implemented because supplementing oxygen could not be suspended) will be summarized by treatment group (number of patients, %).
- 5) A list of outliers in  $\text{PaO}_2$  values on Smirnov-Globus test (significance level of 0.1) in any of the treatment groups will be prepared by time point.

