#### 2.1.2.10.2.7 Changes from baseline in the inflammatory marker (CRP) and cytokines to each time point.

(1) Analysis set : FAS

(2) Analysis item : changes from baseline in the inflammatory marker (CRP) and cytokines (each time point - Day 1)

(3) Time point : Day 1, Day 3, Day 5, at discontinuation/completion of treatment

(4) Analytical method :

- 1) Summary statistics (number of patients, arithmetic mean, standard deviation, median, minimum, maximum) for measured values and changes from baseline in inflammatory marker (CRP), cytokine markers (measured values and log2 log-transformed values of IL-6, IL-1 $\beta$ , TNF- $\alpha$ , IL-10, CCL17, CXCL9, MMP-12) and CXCL9/CCL17 ratios to each time point will be calculated by treatment group and by time point. In addition, a chart for the mean  $\pm$  standard deviation over time will be prepared by treatment group.
- 2) Estimated values of differences between groups, 95% confidence intervals and the p-values (Day 3, Day 5, at discontinuation/completion of treatment) will be calculated using mixed effect model for repeated measures with and changes from baseline in inflammatory marker (CRP) and cytokine markers (measured values and log2 log-transformed values of IL-6, IL-1 $\beta$ , TNF- $\alpha$ , IL-10, CCL17, CXCL9, MMP-12) and CXCL9/CCL17 ratio to each time point as response variables, baseline values as the covariate, time point, treatment group, and time point \* treatment group as the fixed

effects. In addition, a chart for the changes in estimated values and 95% confidence intervals over time will be prepared by treatment group.

2.1.2.10.2.8 Distribution and proportion of patients in each category on a 7-point ordinal scale from Day 0 until Day 28

(1) Analysis set : FAS

(2) Analysis item : 7-point ordinal scale

(3) Time point : Day 0 to Day 28

(4) Analytical method :

1) The number of patients and the proportion in each category on the 7-point ordinal scale shown in Table 2.1 from Day 0 until Day 28 will be summarize by treatment group and by time point (number of patients, %). In addition, a bar chart showing the percentage of each category will be prepared by treatment group and by time point.

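### The MMRM applies one baseline slope to every visit; if slopes differ by visit, some secondary comparisons lose a little precision, and one added term removes the risk

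*SAP*

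**What the plan says.** SAP 4.7 gives the MMRM as "model CHG = BASE [VISIT] [GROUP] [VISIT] * [GROUP] /ddfm = KR", with the covariance line "repeated [VISIT]/ subject = [SUBJECT] type = UN". The only interaction is visit by group.

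The model texts agree with the code:

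- **CRP and cytokines** (2.1.2.10.2.7, item 2; Day 3, Day 5 and end of treatment): "baseline values as the covariate, time point, treatment group, and time point", the last term being crossed with treatment group.
- **Blood gas** (2.1.2.10.2.6, item 3; p-values at Day 5 and end of treatment): "baseline values as the covariate, time point, treatment group, and treatment group", crossed with time point.
- **HRCT** (2.1.2.10.2.5, items 2 and 3; Day 5 and end of treatment): the same structure.
- **A-aDO2** (2.1.2.10.2.1, item 3): the same structure, but with the baseline day among the model's time points: "baseline values as the covariate, time point (Day 1, Day 5, at discontinuation/completion of treatment".

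The single slope is therefore a consistent choice and not a typing slip. The SAP gives no reason for it.

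A-aDO2 and blood gas also have a cLDA model, "model AVAL_ = AVISITN DIF3 DIF5 DIF10/noint s ddfm = kr", which has no baseline covariate and only a random patient intercept. The primary endpoint does not use any of these models: "comparison between groups using the log-rank test with a significance level of 5% will be performed as well".

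**The concern.** The slope of change on baseline at a visit depends on two things: how strongly the visit value correlates with baseline, and how its SD compares with the baseline SD. A single slope fits every visit only if the product of correlation and SD is constant. In an illness that changes over days, either factor may move. Even with a constant correlation, a shrinking SD makes the slopes differ.

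At a visit that the common slope does not fit, part of the baseline variation stays in the residual and the standard error is larger than the collected data allow. A chance baseline difference between the arms is also only partly adjusted away, and with 40 and 20 patients such differences are not negligible. What is at stake is the precision of secondary comparisons, chiefly CRP and the cytokines, whose model covers the most visits.

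**Working it through.** **The plan's own figures.** The documents state no correlation, slope, visit SD or precision for any MMRM endpoint. The only stated performance figure is 82.1% power for the log-rank test (Protocol 18). It reproduces at 82.4% by simulation and does not depend on the MMRM.

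**Inputs.** From the documents: model terms, unstructured covariance, 40 and 20 patients. Assumed: baseline-to-visit correlations ρ, visit SDs s (baseline SD = 1) and between-visit correlations.

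**Formulas (large sample).**

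- Slope at visit t: β_t = ρ_t·s_t − 1
- Residual variance: v_t = s_t²(1 − ρ_t²)
- Common slope: b = 1'Wβ / 1'W1, where W is the inverse residual covariance
- SE ratio, common against visit-specific slope: √[1 + (β_t − b)²/v_t]

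**Three visits** (Day 3, Day 5, exit; between-visit correlations 0.75 for adjacent visits, 0.55 for Day 3 with exit). This layout applies to CRP and cytokines.

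| ρ | s | β | b | SE ratio |
|---|---|---|---|---|
| 0.7/0.5/0.3 | 1/1/1 | −0.30/−0.50/−0.70 | −0.392 | 1.01/1.01/1.05 |
| 0.7/0.5/0.3 | 0.8/0.6/0.5 | −0.44/−0.70/−0.85 | −0.717 | 1.11/1.00/1.04 |
| 0.8/0.5/0.3 | 0.9/0.5/0.4 | −0.28/−0.75/−0.88 | −0.799 | 1.39/1.01/1.02 |
| 0.6/0.6/0.6 | 1/0.7/0.4 | −0.40/−0.58/−0.76 | −0.751 | 1.09/1.05/1.00 |

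Day 3 of the second row: v = 0.64 × 0.51 = 0.3264; (−0.44 + 0.717)² = 0.0767; √(1 + 0.0767/0.3264) = 1.11. Day 3 of the third row: v = 0.81 × 0.36 = 0.2916; (−0.28 + 0.799)² = 0.2695; √(1 + 0.2695/0.2916) = 1.39.

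**Two visits** (Day 5, exit; ρ = 0.5/0.3, between-visit correlation 0.75). This layout applies to HRCT, blood gas and A-aDO2.

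| s | b | SE ratio |
|---|---|---|
| 1/1 | −0.565 | 1.003/1.010 |
| 0.6/0.5 | −0.798 | 1.018/1.006 |
| 0.5/0.4 | −0.844 | 1.023/1.004 |

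**Finite-sample check** (6000 simulated trials per setting, 40 and 20 patients, complete data).

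| ρ | s | SE ratio |
|---|---|---|
| 0.6/0.6 | 1/1 | 1.00/1.00 |
| 0.6/0.4 | 1/1 | 1.00/1.01 |
| 0.7/0.4 | 1/1 | 1.01/1.03 |
| 0.7/0.5/0.4 | 1/1/1 | 1.01/1.01/1.02 |
| 0.7/0.5/0.3 | 1/0.8/0.6 | 1.10/1.00/1.04 |

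The mean treatment difference was within 0.01 SD of the truth throughout.

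**Chance imbalance.** Where slopes differed, a 1 SD baseline imbalance left a shift of 0.03 to 0.34 SD. The standard error of the baseline difference is √(1/40 + 1/20) = 0.27 SD, so a typical imbalance leaves about 0.27 × 0.03 = 0.01 to 0.27 × 0.34 = 0.09 SD.

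**Day 1 in A-aDO2 item 3.** Change at Day 1 is zero for every patient, so its residual variance is zero and the unstructured matrix in the 4.7 code is singular. A common slope would be pulled to 0, leaving an unadjusted change score. With equal SDs its variance relative to the adjusted analysis is 2(1 − ρ)/(1 − ρ²) = 2/(1 + ρ): 1.54, 1.33 and 1.18 for assumed ρ of 0.3, 0.5 and 0.7. A visit-specific slope does not remove the singularity.

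**The case against.** The strongest reply is that nothing in the documents shows unequal slopes. With equal slopes the SE ratio is 1.00 and the plan loses nothing. This stands, and it makes the point conditional.

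A reader might infer from the three-visit table that every MMRM endpoint loses 11% or 39%. The documents do not support that. Those figures arise only at Day 3, and only the CRP and cytokine model makes an MMRM comparison at Day 3. HRCT is read at Day 0, Day 5 and end of treatment, and item 3 for blood gas and A-aDO2 compares the groups at Day 5 and end of treatment. The 39% also needs the correlation to fall from 0.8 to 0.3 while the SD falls from 0.9 to 0.4. Cytokines are analysed on the log2 scale as well as the measured scale, and the documents do not say whether either scale shows such a fall.

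Treating exit as a uniformly later visit is also a simplification. Under footnote 6 of the protocol's schedule, the exit test is done at discontinuation before Day 5, or on the last dosing day when that is not Day 5. Exit therefore mixes early stoppers with patients dosed beyond Day 5.

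The cLDA model does not answer the point. It covers only A-aDO2 and blood gas, and its random intercept also implies a single baseline relation for all visits.

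**Conclusion.** The point holds as a conditional, minor matter of precision in secondary analyses. Under the assumed inputs, the standard error is about 0–5% too large in mild settings. At Day 3 for CRP and cytokines it is about 10% too large if the SD also falls markedly, and 39% only in the extreme case. Where only Day 5 and exit are compared, the inputs above give about 2% at most. That last figure is not a general bound: the two-visit simulation with correlations 0.7/0.4 gave 3%, and more widely spread slopes or a very high between-visit correlation would give more.

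A reader might also infer biased treatment estimates or a threat to the primary result. Neither follows. Randomisation keeps the estimates unbiased on average, and the log-rank analysis and its stated power do not involve this model.

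The Day 1 entry for A-aDO2 does not depend on assumed slopes. If the 4.7 MMRM code is applied to the time points as listed, the covariance is singular.

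**What to change.** - In SAP 4.7, change the MODEL statement to CHG = BASE [VISIT] BASE*[VISIT] [GROUP] [VISIT]*[GROUP].
- Add baseline-by-time-point to the fixed effects in 2.1.2.10.2.1 item 3, 2.1.2.10.2.5 items 2 and 3, 2.1.2.10.2.6 item 3 and 2.1.2.10.2.7 item 2.
- In 2.1.2.10.2.1 item 3, remove Day 1 from the response time points and keep it only as the baseline covariate. The added interaction does not cure this by itself.

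The cost is one degree of freedom with two post-baseline visits and two with three, plus the text edits. No new data are needed. If the slopes turn out equal, almost nothing is lost.
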